Stage related to study timeline	A major subdivision of the study timeline; begins and ends with major study milestones such as enrollment, randomization, completion of treatment, etc.
Stop study participation	Point/time at which the patient came in for a final evaluation visit or when study treatment was discontinued whichever is later
Study treatment	Includes any drug or combination of drugs in any study arm administered to the patient (subject) as part of the required study procedures, including placebo and active drug run-ins. In specific examples, it is important to judge investigational treatment component relationship relative to a study treatment combination; study treatment in this case refers to the investigational and non-investigational treatments in combination.
Study treatment discontinuation	Point/time when patient permanently stops taking study treatment for any reason
Variable	Identifier used in the data analysis; derived directly or indirectly from data collected using specified assessments at specified timepoints
Withdrawal of consent	Withdrawal of consent occurs only when a patient does not want to participate in the study any longer, and does not want any further visits or assessments, and does not want any further study related contact

Protocol summary:

Title	A multicenter phase II, open label, single arm study to evaluate the efficacy and safety of ruxolitinib in the treatment of anemic myelofibrosis patients.
Brief title	Anemia trial in MF patients
Sponsor and Clinical Phase	Novartis Phase II
Investigation type	Drug
Study type	Interventional
Purpose and rationale	This is a study of treatment with ruxolitinib in patients who present with transfusion dependent or independent anemia at screening defined as an hemoglobin <10 g/dL with 10 mg BID starting dose with subsequent up titrations depending on safety and efficacy. This dosing approach for anemic MF patients will be systematically studied in this prospective multicenter phase II open label single arm trial to determine if the levels of spleen length reduction and symptom improvement are consistent with those reported in previous clinical trials with ruxolitinib in patients with anemia and doses according to platelet counts at the moment of treatment initiation, and whether this lower starting dose and up titration approach may minimize the initial hemoglobin and platelet declines and transfusion requirements.

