5.3 Exclusion criteria

Patients eligible for this study must not meet **any** of the following criteria:

1. Patients with prior treatment with any JAK1 or JAK2 inhibitor.
2. Patients with known hypersensitivity to ruxolitinib or other JAK1/JAK2 inhibitors, or to their excipients.
3. Patients eligible for hematopoietic stem cell transplantation (suitable candidate and a suitable donor is available).
4. Patients with inadequate bone marrow reserve at baseline as demonstrated by at least one of the following:
 - a. ANC that is $\leq 1,000/\mu\text{L}$.
 - b. Platelet count that is $< 50,000/\mu\text{L}$ without the assistance of growth factors, thrombopoietic factors or platelet transfusions.
 - c. Hemoglobin count that is ≤ 6.5 g/dL despite transfusions.
5. Patients with severely impaired renal function defined by:
Creatinine clearance less than 30 mL/min.
6. Patients with inadequate liver function defined by any of these:
 - a. Total bilirubin ≥ 2.5 x ULN and subsequent determination of direct bilirubin ≥ 2.5 x ULN;
 - b. Alanine aminotransferase (ALT) > 2.5 x ULN;
 - c. Aspartate aminotransferase (AST) > 2.5 x ULN.
7. Patients being treated concurrently with a strong (potent) systemic inhibitor or inducer of CYP3A4 at the time of Screening.
8. Presence of active bacterial, fungal, parasitic, or viral infection which requires therapy.
9. Known history of human immunodeficiency virus (HIV) infection or other immunodeficiency syndromes such as X-linked agammaglobulinemia and common variable immune deficiency.

10. Acute viral hepatitis or active chronic hepatitis B or C infection. Patients with *inactive* chronic infection (without viral replication) can be enrolled (See [Section 7.2.2.7](#))
11. History of progressive multifocal leuko-encephalopathy (PML).
12. Impairment of gastrointestinal (GI) function or GI disease that may significantly alter the absorption of ruxolitinib (e.g., ulcerative diseases, uncontrolled nausea, vomiting, diarrhea, malabsorption syndrome, small bowel resection).
13. History or current diagnosis of uncontrolled or significant cardiac disease, including any of the following:
 - a. Myocardial infarction within last 6 months
 - b. Uncontrolled congestive heart failure
 - c. Unstable angina within last 6 months
 - d. Clinically significant (symptomatic) cardiac arrhythmias (e.g. bradyarrhythmias, sustained ventricular tachycardia, and clinically significant second or third degree AV block without a pacemaker)

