6.3.5 Restarting or reinstating previous dose

Dosing of ruxolitinib may be restarted or increased following recovery of platelet counts and/or ANC to acceptable levels as illustrated in [Table 6-3](#). The objective for restarting or

escalating after a reduction for safety is to find the highest safe dose of ruxolitinib for each patient, with increases in dose generally not more than in increments of 5 mg BID and not more often than every 2 weeks. Similarly, ANC levels that decline to < 500/ μ L necessitate immediate dose interruption ([Section 6.3.1.1](#)). ANC level recovery to 500 / μ L and above but less than 750/ μ L will allow dosing to be restarted at 5 mg BID, and ANC levels between 750/ μ L, but < 1000/ μ L may restart at 10 mg BID. Absolute neutrophil count level increases to above 1000/ μ L will allow a further dose increase.

[figure not shown]
After restarting using the guidelines in [Table 6-3](#), if it is found that a patient cannot tolerate the lowest allowed dose (5mg BID, or 5mg QD with concomitant CYP3A4 inhibitor, see [Section 6.4.2](#)) without platelets falling below 25,000/ μ L, neutrophils falling below 500/ μ L, or Hgb falling below 6.5g/dL despite the use of transfusion therapy, drug must be permanently discontinued ([Section 6.3.1.1](#)).

Table 6-3 Restarting or reinstating previous ruxolitinib dose after safety interruptions or dose reductions

Current Platelet Count after interruption or reduction	Maximum Dose for Restarting or reinstating previous dose after interruption or reduction
< 25,000/ μ L	Continue hold
25,000/ μ L to < 50,000/ μ L	5 mg BID
50,000/ μ L to < 75,000/ μ L	10 mg BID
75,000/ μ L to < 125,000/ μ L	15 mg BID
\geq 125,000/ μ L	20 mg BID
Current ANC Level after interruption or reduction	Dose Restart or Dose Increase Guidelines
< 500/ μ L	Continue hold
500 to < 750/ μ L	5 mg BID for at least 2 weeks; if stable, may increase to 10 mg BID
750 to < 1000/ μ L	10 mg BID for at least 2 weeks; if stable, may increase to 15 mg BID
1000 to < 1500/ μ L	15 mg BID for at least 2 weeks; if stable may increase to 20 mg BID
\geq 1500/ μ L	20 mg BID
NOTE: Whether the dose interruption occurred because of neutropenia, thrombocytopenia or both, when restarting, both the platelet count and ANC must be considered to determine the restart dose, with the lower calculated dose being used.	

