6.4.2 Permitted concomitant therapy requiring caution and/or action

The following medications have restrictions on use, dose, or require changes to the way in which ruxolitinib is administered during the study:

- In patients for whom warfarin or heparin use will be initiated, the degree of thrombocytopenia should be considered, coagulation parameters monitored, and dose of anticoagulant adjusted accordingly. If anticoagulation is required during ruxolitinib administration, low molecular weight heparin is preferred, particularly in patients who are: elderly, history of CHF, diabetic, hepatic or renal disease, or atrial fibrillation (first episode).
- Low dose aspirin (≤ 150 mg/day) and non-steroidal anti-inflammatory agents (acetaminophen, ibuprofen) may be used. Aspirin doses > 150 mg are prohibited.
- Inducers or inhibitors of the metabolizing enzyme CYP3A4 (Appendix 5)
- When concomitant administration of a strong (potent) inhibitor of CYP3A4 metabolizing enzymes or dual CYP2C9/CYP3A4 inhibitors (Appendix 5) is required for patient management, the dose of ruxolitinib tablets must be reduced by approximately 50% to be administered twice daily by decreasing the twice daily dose or by decreasing the frequency of dosing to the corresponding once daily dose when twice daily dose is not practical.
 - Note: No dose adjustment of ruxolitinib is needed for use with topical ketoconazole.

- Note: More frequent monitoring of hematology parameters and clinical signs and symptoms of ruxolitinib related adverse reactions is recommended upon initiation of a strong (potent) CYP3A4 inhibitor.
- No dose adjustment will be made when moderate systemic CYP3A4 inducers ([Appendix 5](#)) are co-administered with study treatment.
- Granulocyte growth factors are not allowed while study treatment is being administered but may be used for severe neutropenia at the Investigator's discretion while study medication is being withheld.
- Certain herbal supplements see [Appendix 5](#) are prohibited. Because the composition, pharmacokinetics and metabolism of many herbal supplements are unknown, the concurrent use of all herbal supplements is strongly discouraged during the study however if used during the trial please ensure the treatment is entered on the proper eCRF page (see [Section 6.4.1](#)).

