7.2.2.3 Transfusion requirements

At the screening visit, information on all prior transfusions (Whole blood - PRBC) performed during the last 12 weeks prior to screening will be collected and recorded in the appropriate eCRF.

At each subsequent visit, all transfusions (Whole blood - PRBC) performed since the last visit will be collected and recorded in the appropriate eCRF.

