In the phase 3 clinical studies in MF, in patients who developed grade 3 or 4 thrombocytopenia, the median time to onset was approximately 8 weeks. Thrombocytopenia was generally reversible with dose reduction or dose interruption. The median time to recovery of platelet counts above 50,000/mm³

was 14 days. During the randomised period, platelet transfusions were administered to 4.7% of patients receiving Jakavi and to 4.0% of patients receiving control regimens. Discontinuation of treatment because of thrombocytopenia occurred in 0.7% of patients receiving Jakavi and 0.9% of patients receiving control regimens. Patients with a platelet count of 100,000/mm³ to 200,000/mm³ before starting Jakavi had a higher frequency of grade 3 or 4 thrombocytopenia compared to patients with platelet count >200,000/mm³ (64.2% versus 38.5%).

In the randomised period of the pivotal studies, the rate of patients experiencing thrombocytopenia was lower in PV (24.5%) patients compared to MF (69.8%) patients. The frequency of severe (i.e. CTCAE grade 3 and 4) thrombocytopenia was lower in PV (5.5%) than in MF (11.6%) patients.

Neutropenia

In the phase 3 clinical studies in MF, in patients who developed grade 3 or 4 neutropenia, the median time to onset was 12 weeks. During the randomised period, dose holding or reductions due to neutropenia were reported in 1.0% of patients, and 0.3% of patients discontinued treatment because of neutropenia.

In the randomised period of the pivotal study in PV patients, neutropenia was reported in two patients (1.8%) of which one patient developed CTCAE grade 4 neutropenia.

Bleeding

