Clinical Development

INC424/ruxolitinib/Jakavi®

REALISE (CINC424A2411) / NCT02966353

A multicenter phase II, open label, single arm study to evaluate the efficacy and safety of Ruxolitinib in the treatment of anemic myelofibrosis patients.

Statistical Analysis Plan (SAP) Amendment 1

Author: Trial Statistician, [REDACTED]

Document type: SAP Documentation

Document status: Final

Release date: 12-Mar-2019

Number of pages: 29

Property of Novartis

For business use only

May not be used, divulged, published or otherwise disclosed
without the consent of Novartis

Document History – Changes compared to previous final version of SAP

Date	Time point	Reason for update	Outcome for update	Section and title impacted (Current)
12 Mar 2019	Before DBL	To modify windowing rules	Analysis table modified to exclude EOT in visit window	Section 2.1.1
		To remove text	Removed text for “Significant non-drug therapies” as it is not captured in the study	Section 2.4.2
		To add Spleen response definition and analysis by IWG-MRT criteria and also to add an analysis for primary endpoint at any time during the study.	Add definition and analysis of spleen response as per IWG MRT Criteria as per the recommendation from steering committee	Section 2.5.4
		To add an analysis on transfusion requirements and modify some text	Added clarification that unit of blood transfusion will be used for analysis and not the episode of transfusion; An analysis for transfusion dependent rate added for patient who were not TD at baseline	Section 2.7.2
		To add some decription on Adverse Event of Specail Interest (AESI)	Add a breif discription on AESI and a listing is proposed for AESI	Section 2.8.1.1
		To remove analysis	Shift tables based on low/normal/high ranges removed	Section 2.8.3
		To remove analysis	Shift table for baseline ECOG score vs worst post-baseline ECOG score removed. ECOG score over time will only be listed	Section 2.8.4.2
		To add description of PRO related derivations and few analysis	Added analysis on PRO similar to spleen response at Week 24	Section 2.11

Date	Time point	Reason for update	Outcome for update	Section and title impacted (Current)
		To add description of DIPSS score calculation	Added definition and criteria to calculate DIPSS risk scores and risk groups	Section 5

Table of contents

Table of contents	4
List of abbreviations	6
1 Introduction	8
1.1 Study design.....	8
1.2 Study objectives and endpoints	8
2 Statistical methods.....	9

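### Platelet transfusions have no assured dated record, so platelet counts taken after one cannot be flagged and no platelet-transfusion rate can be reported

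*Protocol*

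**What the plan says.** **Recording.** Protocol section 7.2.2.3 collects at screening "information on all prior transfusions (Whole blood - PRBC) performed during the last 12 weeks prior to screening", and at each later visit "all transfusions (Whole blood - PRBC) performed since the last visit will be collected". Platelets are not named in either sentence. Section 6.4.1 is broader: it counts blood transfusions, with no product named, among the significant non-drug therapies to be listed on a CRF. The SAP document history, however, records that text on significant non-drug therapies was taken out of SAP section 2.4.2 "as it is not captured in the study". The current section 2.4.2 summarises concomitant medications only, yet it still promises a listing of such therapies that ended before treatment began.

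**Aim and analysis.** The Protocol summary and section 2.2 ask whether the regimen "may minimize the initial hemoglobin and platelet declines and transfusion requirements". SAP section 2.8.3 plans hematology changes from baseline over time, box plots by time window, worst post-baseline grades and shift tables. Neither document plans a platelet-transfusion output or a marker for counts that follow a transfusion.

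**Use of the platelet count.** Exclusion criterion 4b in Protocol section 5.3 judges the entry platelet count "without the assistance of growth factors, thrombopoietic factors or platelet transfusions". On study, the platelet count helps to determine up-titration (6.2.3), dose reduction (Table 6-2) and restart (section 6.3.5, Table 6-3). For restart, "both the platelet count and ANC must be considered to determine the restart dose". None of these rules says whether the platelet count has to be unsupported.

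**The concern.** A platelet transfusion raises the count for a time. If it has no date on file, a later platelet value looks the same as the patient's own count. The summaries of platelet change over time are then mixed in a way that cannot be undone at analysis, and the trial cannot report how many patients needed platelet support. Both matter because platelet decline is part of the question the trial sets itself. The screening history has the same gap, so criterion 4b cannot be checked against a structured record either.

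The second strand concerns wording. A site that holds a post-transfusion count at a dose decision finds no statement of whether it may be used, whereas the entry criterion is explicit and the hemoglobin rules do mention transfusion support.

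**Working it through.** The plan states no figure on this point, so there is none to reproduce. The check sets the passages side by side and then gives a scale.

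**1. Is there a dated platelet-transfusion record?**
- Dedicated record (Protocol 7.2.2.3): whole blood and PRBC only, at screening and at each visit.
- General record (Protocol 6.4.1): blood transfusions on a CRF, product not limited. The SAP document history says that category is not captured. A change log does not govern the analysis, but this line is a statement about the data, and the current section 2.4.2 agrees with it for the on-treatment period.
- Adverse-event record (Protocol 8.1.1): a hematologic abnormality that needs transfusion is an adverse event, with start and end dates and grade. The therapy item is a category (medication or non-drug therapy, or neither); the section asks for no product, transfusion date or units. The SAP section 2.8.1 table of events needing additional therapy inherits that limit.

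Result: the need for transfusion is visible, but a given platelet value cannot be linked to a preceding transfusion.

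**2. Which outputs are exposed?**
- Changes over time and box plots: exposed. SAP section 2.1.1 picks the assessment closest to the target day within each window, so a post-transfusion value can be the one used.
- Worst-grade and shift tables: largely protected. A recorded nadir is not displaced by a later, higher count.
- Week 24 decision rule (at least 13 responders of 50): not exposed. It counts spleen-length responders and uses no platelet value.

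**3. Scale.** Inputs: n = 50 (Protocol 10.8). For the phase 3 myelofibrosis studies the label in Protocol Appendix 6, section 4.8, reports that "platelet transfusions were administered to 4.7% of patients receiving Jakavi", against 4.0% on control regimens.
- Expected number = n × p; chance of at least one = 1 − (1 − p)^n.
- p = 0.047: 50 × 0.047 = 2.35 patients; 1 − 0.953^50 = 0.91.
- p = 0.02 (assumed): 50 × 0.02 = 1.0; 1 − 0.98^50 = 0.64.
- p = 0.10 (assumed): 50 × 0.10 = 5.0; 1 − 0.90^50 = 0.995.

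The true rate could lie on either side of 4.7%. This trial admits platelet counts from 50,000/µL, while the phase 3 strata began at 100,000/µL. Against that, it starts at 10 mg BID, while phase 3 started at 15 or 20 mg BID. The documents give no rate for this population.

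**4. Dose-rule wording.**
- Support: criterion 4b speaks of it for platelets; sections 6.2.3 and 6.3.1.1 (Table 6-2) and Table 6-3 are silent.
- Restart: section 6.3.1.1 makes 5 mg twice daily mandatory after an interruption. Section 6.3.5 and Table 6-3 set the restart dose by count and allow more than that. The heading of the platelet column calls its entries maxima, which could be read as compatible. The ANC text, which allows a restart at 10 mg BID from 750/µL, cannot. The two sections contradict each other.

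**The case against.** The strongest reply is that the restriction to red-cell products fits its purpose. Section 7.2.2.3 feeds the transfusion-dependence and transfusion-independence endpoints of an anemia trial, for which whole blood and PRBC are the relevant products. That stands: the restriction is no error for those endpoints. It does not help the platelet question, which the plan also raises.

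It can also be said that the eCRF itself is not in the documents, and that section 6.4.1 may lead sites to record platelet transfusions somewhere. That is fair, and it is why the conclusion is that there is no assured record, not that none can exist.

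A reader might infer several stronger things that the documents do not support.
- *That platelet toxicity would be hidden.* Thrombocytopenia needing transfusion is a reportable adverse event, platelets are measured at every visit, all assessments are listed, and nadirs stay in the worst-grade tables.
- *That the dose rules accept supported counts.* They are silent. An entry criterion and a titration rule may differ in wording without contradiction.
- *That a supported count would raise the restart dose.* Section 6.3.1.1 fixes the restart at 5 mg twice daily. What the documents show is the conflict with Table 6-3, not a definite higher dose.
- *That growth-factor-supported ANC values have the same gap.* Section 6.4.2 bars granulocyte growth factors during dosing; they "may be used for severe neutropenia at the Investigator's discretion while study medication is being withheld". So the matter touches restart only. Criterion 4b concerns platelets, and 4a sets no such condition for ANC. These agents are medications and are already recorded.
- *That 91% is the chance of a wrong dose or table.* It is the chance that at least one of 50 patients receives any platelet transfusion. How often one would fall close enough to a visit to matter is not known.

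**Conclusion.** The point holds as a gap in data collection with a limited effect. As written, the plan assures no platelet-transfusion record with date and units. The loss is the ability to flag supported counts in the over-time platelet summaries and to report a platelet-transfusion rate. About 2.4 of 50 patients would be involved at the label's 4.7%, and 1 to 5 over an assumed 2% to 10%. This assumes that the phase 3 rate is a fair guide and that sites follow section 7.2.2.3 as worded. No primary result or decision threshold changes.

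Separately, three sets of passages need reconciling: sections 6.4.1 and 7.2.2.3 with the SAP statement on what is captured; criterion 4b with the on-study platelet rules, on whether support matters; and section 6.3.1.1 with section 6.3.5 and Table 6-3, on the restart dose. This is a cheap improvement of low priority.

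**What to change.** (a) **Data and analysis.** Add platelet transfusions, with date and units, to section 7.2.2.3 and to the existing transfusion eCRF page, for the 12-week history and for each visit. Keep the product type as a separate field, and say in SAP section 2.7.2 that only red-cell products count toward transfusion dependence, independence and response, so that platelet units do not enter those derivations. In SAP section 2.8.3, flag platelet values that follow a platelet transfusion in the over-time summaries and box plots, and report the number of patients given platelet transfusions. Bring section 6.4.1, section 7.2.2.3 and SAP section 2.4.2 into agreement on what is recorded.

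(b) **Wording.** State in sections 6.2.3, 6.3.1.1 and 6.3.5 whether supported platelet counts may be used, so that the relation to criterion 4b is clear, and remove the contradiction on restart dose between section 6.3.1.1 and section 6.3.5 with Table 6-3. Which rule applies is for the sponsor's clinical team.

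The cost is one product category on a page already completed at each visit, one flag, one table row and a few clarifying sentences. The downside is slightly more data entry.

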7.2.2.4 Vital signs

Vital signs include blood pressure and body temperature measurement.

7.2.2.5 Height and weight

Height will be measured at screening.

[figure not shown]
Body weight (in indoor clothing, but without shoes) will be measured at screening and at subsequent time points as specified in [Table 7-1](#).

